11.6.2 Secondary Analyses

11.6.2.1 Pharmacokinetics

The secondary PK parameters from Group-1 PK population (AUC_(0-t'), AUC_(0-∞), %AUC_{extrap}, t_{last} , t_{max} , λ_z and $t_{\frac{1}{2}}$) and all the PK parameters from Group-2 PK population $(C_{max}, AUC_{(0-last)}, AUC_{(0-t')}, AUC_{(0-\infty)}, %AUC_{extrap}, t_{last}, t_{max}, \lambda_z \text{ and } t_{\frac{1}{2}})$ will be listed and summarized as described in Section 11.1 "General Considerations" and subsections. In addition plots of the data versus product will be provided.

The nicotine plasma concentrations will be summarized in a similar manner to the PK parameters but will also be split out by sample time point. Geometric mean (95% CI) profiles, spaghetti plots of all subjects and individual PK profiles for each subject will also be presented.

PK parameter and plasma concentration data will also be listed along with the details of the actual times after T_0 .

Statistical Analysis Plan Final v 2.0 / 07 April 2014 Confidential
Page 45 of 73

TFL number	Title	
TABLES		
15.2.4.5	Descriptive Statistics of Pharmacokinetic Parameters of Nicotine – PK Population	
15.2.4.5.1	Descriptive Statistics of Pharmacokinetic Parameters of Nicotine by Sex – PK Population	
15.2.4.5.2	Descriptive Statistics of Pharmacokinetic Parameters of Nicotine by Nicotine Level – PK Population	
15.2.4.6	Descriptive Statistics of Plasma Nicotine Concentrations (ng/mL)– PK Population	
15.2.4.6.1	Descriptive Statistics of Plasma Nicotine Concentrations (ng/mL) by Sex – PK Population	
15.2.4.6.2	Descriptive Statistics of Plasma Nicotine Concentrations (ng/mL) by Nicotine Level – PK Population	
FIGURES	Section of the sectio	
15.1.2.1.1	Nicotine Plasma Concentration (ng/mL) Profiles Geometric Mean and 95% CI – Group-1 PK Population	
15.1.2.1.2	Nicotine Plasma Concentration (ng/mL) Profiles Geometric Mean and 95% CI – Group-2 PK Population	
15.1.2.2.1	Nicotine Plasma Concentration (ng/mL) Profiles for All Subjects – Group-1 PK Population	
15.1.2.2.2	Nicotine Plasma Concentration (ng/mL) Profiles for All Subjects – Group-2 PK Population	
15.1.2.3	Nicotine Plasma Concentration (ng/mL) Profiles by Subject – PK Population	
15.1.2.4	Secondary Pharmacokinetic Parameters of Nicotine – Group-1 PK Population	
15.1.2.5	Pharmacokinetic Parameters of Nicotine – Group-2 PK Population	
LISTINGS	The state of the s	
15.3.3.1	Listing of Pharmacokinetic Parameters of Nicotine – Safety Population	
15.3.3.2	Listing of Plasma Nicotine Concentrations (ng/mL) and Sampling Times – Safety Population	
15.3.3.3	Listing of Additional Pharmacokinetic Parameter Data – Safety Population	

11.6.2.1.1 THS 2.2 vs CC

Only subjects in the Group-1 PK population will be included in the following analyses.

The secondary analysis of AUC_(0-∞), AUC_(0-t') and t_½ will be performed on the natural log-transformed parameters using the same ANOVA model as used for the primary analysis. (Section 11.6.1 "Primary Analyses"). Only subjects in the Group 1-PK population who provide evaluable data for both the THS 2.2 and CC products will be included in the analyses.

Statistical Analysis Plan Final v 2.0 / 07 April 2014 Confidential

Page 46 of 73

Supportive analysis will be performed as described in Section 11.6.3 "Supportive/Sensitivity Analysis" in order to evaluate the sensitivity of THS 2.2 effect estimates to methods used for missing data by means of a mixed model approach, should there be 20% or more missing parameter PK model.

The analysis of t_{max} will be performed by calculating the difference for each subject (THS 2.2 - CC) and obtaining the Hodges-Lehmann (Hodges and **Lehmann**, 1963) 95% CI estimates. The median t_{max} for each product and the median difference between the products along with the 95% CI will be presented in the tables. Supportive analysis will be performed as described in Section 11.6.3 "Supportive/Sensitivity Analysis" in order to evaluate the THS 2.2 effect estimates on t_{max} adjusted for period, sequence, and subject within sequence.

The data will be presented in the below outputs:

TFL	Title
number	
TABLES	
15.2.4.1	Analysis of Secondary Pharmacokinetic Parameters of Nicotine -
	Group-1 PK Population

11.6.2.1.2 THS 2.2 vs NRT gum

The following analyses will be conducted in only Group-2 PK population:

The secondary analysis of C_{max} , $AUC_{(0-last)}$, $AUC_{(0-\infty)}$, $AUC_{(0-t')}$ and $t_{1/2}$ parameters will be performed parameters using the same ANOVA model as used for the primary analysis. (Section 11.6.1 "Primary Analyses").

Only subjects in the Group-2 PK population who provide evaluable data for both the THS 2.2 and CC products will be included in the analyses.

The analysis of C_{max} and AUC_(0-last) will test if the lower bound of the 95% CI for the ratio (THS 2.2 : NRT gum) is > 1.0 at the 0.025 level of significance in order to determine if the rate and the amount of nicotine absorbed of the THS 2.2 is higher relative to NRT gum. This approach will be used to test the following hypothesis for both C_{max} and $AUC_{(0-last)}$ parameters:

$$H_0$$
: $X_{THS} / X_{NRT} = 1.0$
 H_A : $X_{THS} / X_{NRT} > 1.0$

where X_{THS} and X_{NRT} are the adjusted geometrical means of THS 2.2 and NRT gum, respectively. H_0 is rejected with a type I error $\alpha = 0.025$ (one-sided test).

Statistical Analysis Plan Final v 2.0 / 07 April 2014 Confidential

Page 47 of 73

 To test if the time to the maximum nicotine concentration in THS 2.2 is shorter than in NRT gum the following hypothesis will be evaluated:

$$H_0$$
: X_{THS} - $X_{NRT} = 0$
 H_A : X_{THS} - $X_{NRT} < 0$

where X_{THS} and X_{NRT} are the median values of the THS 2.2 and NRT gum, respectively. t_{max} will be analysed on the original scale using the Wilcoxon Signed-Rank Test with a type I error $\alpha=0.025$ (one-sided test), as values are ordinal/discrete, and the assumption of normality may be questionable.

The analysis of t_{max} will be performed by calculating the difference for each subject (THS 2.2 – NRT gum) and obtaining the Hodges-Lehmann 95% CI estimates (**Hodges and Lehmann, 1963**). The median t_{max} for each product and the median difference between the products along with the 95% CI will be presented.

Supportive analysis will be performed as described in Section 11.6.3 "Supportive/Sensitivity Analysis".

The data will be presented in the below outputs:

Title
Analysis of Pharmacokinetic Parameters of Nicotine – Group-2 PK Population

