12 PLANNED STATISTICAL METHODS

12.1 General Considerations

An incomplete block design will be adopted in this study with every subject being exposed to 2 out of the 3 study products (CC, THS 2.2, and NRT gum) to allow comparisons between THS 2.2 and CC in Group-1 (sequence 1 and 2), and between THS 2.2 and NRT gum in Group-2 (sequence 3 and 4).

Full details of the statistical analysis will be given in a SAP. Any changes to the planned statistical methods will be documented in the Clinical Study Report. The statistical evaluation will be performed using SAS[®], version 9.2 or later.

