12.6.3 Descriptive Analysis

In general, secondary endpoints will be summarized using the approach described in Section 12.1.3.

The following analyses will be conducted in both Group-1 and Group-2 PK analysis sets:

- The AUC_(0- ∞), AUC_(0-t'), and t_{1/2} will be analyzed using the same approach adopted for the primary endpoints. No statistical analysis will be performed on the elimination rate constant λ_z . Data will be summarized and presented together with 95% CI.
- The Hodges-Lehmann 95% CI estimates for the median t_{max} differences will be presented (Lingling, 2008).
- The use of random effects model is suggested in the context of the analysis of subjective effects of smoking (Shiffman et al., 2004). Mixed effects ANOVA with the same model terms as planned for the sensitivity analysis of the primary endpoints will be adopted for the analysis of QSU-brief, including all of the different assessment time points as repeated measurements. The analysis will not be adjusted for the assessment prior to T₀ (Fleiss et al, 1985).
- Levels of exhaled CO and of blood COHb will be summarized by means of descriptive statistics reported by exposure. Analysis of COHb levels will be conducted using a mixed model for repeated measures, the same approach as for the QSU-brief.

The following analyses will be conducted only in Group-1 PK analysis set:

• Mixed effects ANOVA with the same model terms as planned for the sensitivity analysis of the primary endpoints will be adopted for the analysis of the MCEQ domain scores.

The following analyses will be conducted in only Group-2 PK analysis set:

• To test if the time to the maximum nicotine concentration in THS 2.2 is shorter than in NRT gum the following hypothesis will be evaluated:

Philip Morris Products S.A.	Clinical Study Protocol	Confidential
ZRHR-PK-02-JP	Final 1.0 / 21 June 2013	Page 95 of 122

 $H_0: X_{THS} - X_{NRT} = 0$ $H_A: X_{THS} - X_{NRT} < 0$

where X_{THS} and X_{NRT} are the median values of the THS 2.2 and NRT gum, respectively. The t_{max} will be analyzed on the original scale using the Wilcoxon Signed-Rank Test with a type I error $\alpha = 0.025$ (one-sided test), as values are ordinal/discrete, and the assumption of normality may be questionable.

• To determine if the rate and the amount of nicotine absorbed of the THS 2.2 is higher relative to NRT gum the following hypothesis will be tested for both C_{max} and AUC_(0-last) parameters:

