5 STUDY OBJECTIVES AND ENDPOINTS

The endpoints specify randomization groups (Group-1 or Group-2) that are being analyzed for the objective when it is not applied to both (the randomization groups are defined in Table 1 of Section 6.1).

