6 INVESTIGATIONAL PLAN

6.1 Study Design

This is a randomized, controlled, 2-period, 4-sequence, single-use crossover study. An incomplete block design has been adopted, where each subject will receive only two of the three products (Figure 1):

- THS 2.2
- CC

Statistical Analysis Plan Final v 2.0 / 07 April 2014 Confidential
Page 13 of 73

NRT gum

In total, 62 eligible, healthy smoking subjects will be randomized into one of the 4 sequences in Table 1:

Table 1 Definition of Randomization Groups and Sequences

Group	Allocation Ratio	Sequence	Sample Size
Crown 1 = THS 2 2 vs. CC	2.2	1. THS 2.2 then CC	22
Group-1 = THS 2.2 vs. CC	2:2	2. CC then THS 2.2	22
Group-2 = THS 2.2 vs. NRT	1:1	THS 2.2 then NRT gum	9
gum	1:1	4. NRT gum then THS 2.2	9

A Screening Visit will be conducted within 4 weeks prior to Admission to the investigational site (Day -29 to Day -2). A demonstration of the THS 2.2 product and the NRT gum will also be done by the site study collaborator during the screening visit. Subjects will be admitted to the clinic on Day -1 (Admission). On Day -1, as the last procedure of the eligibility assessments on that day, all subjects will undergo a product test prior to enrolment, first THS 2.2 (using of up to 3 Tobacco Sticks) and subsequently NRT gum. In female subjects, the urine pregnancy test must be negative before any product test is performed with either the THS 2.2 or the NRT gum. After all inclusion and exclusion criteria have been satisfactorily met, only subjects willing and ready to use both the THS 2.2 and the NRT gum products can be enrolled. Screening procedures do not necessarily have to be conducted on the same day.

[figure not shown]
Subjects are enrolled on Day -1, but not randomized until the Day 0 washout, therefore it is possible to have enrolled subjects who do not get randomized.

Subjects will be discharged from the investigational site in the morning of Day 4 after all safety examinations of the Day of Discharge have been conducted. After Discharge, subjects will enter into a 7-day safety follow-up to capture spontaneously reported new AEs/SAEs and for active follow-up of ongoing AEs/SAEs. Any AE will in general be followed up until resolved, stabilized i.e., no worsening of the event, or until a plausible explanation for the event has been found.

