6.3 Product Allocation and Blinding

6.3.1 Methods of Assigning Subjects to Treatment Sequences

Randomization will be conducted through the Interactive Web and Voice Response System (IXRS).

Subjects will be randomized to either Group-1 (sequence 1 and 2) or to Group-2 (sequence 3 and 4). Each stratum: sex (male and female) and CC nicotine level at Admission (International Organization for Standardization [ISO] nicotine level \leq 0.6 mg and >0.6 \leq 1 mg) will have a quota applied to ensure they represent at least 40% of the total study population. See Table 1.

To accomplish the above, the subject randomization list will contain randomization records for the 2 groups. A blocked randomization will be used. Subjects will be assigned to the next available sequence providing the quotas have not been met. Block size and other randomization details are available in the randomization plan.

The randomization scheme will be generated by the statistical division within and none of the study team, including study sponsor, (b) (4) and PI or the study subjects will be exposed to the live randomization codes prior to randomization.

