10.1 PK Populations

The analysis populations for the PK endpoints are composed of two populations to allow the comparison between THS 2.2 and NRT gum (Group-1 PK) separately from the comparison between THS 2.2 and CC (Group-2 PK).

The PK populations consist of all the randomized subjects who give informed consent, completed at least one of the single use days (Day 1 or Day 3), and for whom at least one PK parameter can be derived. Only subjects with major protocol deviations that impact the evaluability of the results (see Section 10.3 "Protocol Deviations") will be excluded in the PK populations.

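### SAP 11.6.2.1.2 admits to the THS 2.2 vs NRT gum analyses only subjects with CC data (0 of 18 planned), and SAP 10.1 swaps the Group-1 and Group-2 PK labels

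*SAP*

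**What the plan says.** SAP 11.6.2.1.2 is headed as the comparison of THS 2.2 with NRT gum. It lists five parameters for the ANOVA (C_max, AUC_(0-last), AUC_(0-∞), AUC_(0-t') and t½) and then gives the inclusion rule: "Only subjects in the Group-2 PK population who provide evaluable data for both the THS 2.2 and CC products will be included". The hypotheses that follow concern the ratio of THS 2.2 to gum.

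SAP 11.6.2.1.1, on THS 2.2 against CC, has almost the same sentence: "Only subjects in the Group 1-PK population who provide evaluable data for both the THS 2.2 and CC products". There it fits.

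On the labels, SAP section 5 says that "the randomization groups are defined in Table 1 of Section 6.1". That table has "Group-1 = THS 2.2 vs. CC" with 22 + 22 subjects, and assigns Group-2 to THS 2.2 against gum with 9 + 9. SAP 6.3.1 agrees: "Subjects will be randomized to either Group-1 (sequence 1 and 2) or to Group-2 (sequence 3 and 4"). Protocol 12.1 places the comparison "between THS 2.2 and NRT gum in Group-2 (sequence 3 and 4"), and Protocol 12.6.3 introduces the tests against gum with "The following analyses will be conducted in only Group-2 PK analysis set".

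SAP 10.1, the section that defines the PK populations, says the opposite. It separates the "comparison between THS 2.2 and NRT gum (Group-1 PK) separately from the comparison between THS 2.2 and CC (Group-2 PK").

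SAP section 9, which lists the departures from the protocol's analysis, mentions neither point.

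**The concern.** Both statements decide which subjects enter an analysis.

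The rule in 11.6.2.1.2 asks for a product that Group-2 subjects do not use on a single-use day. Its closeness to the sentence in 11.6.2.1.1 suggests that CC was carried over when the text was copied. That is an inference.

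The label error sits in the population definition, where a programmer looks first. At stake are the C_max and AUC_(0-last) tests against gum. Followed to the letter, the rule gives an empty or non-estimable analysis, so the analyst has to depart from an approved SAP or choose between its contradictory statements.

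**Working it through.** **The plan's own figure.** SAP section 8 plans 18 subjects for the gum comparison: AUC_(0-last) ratio 1.28, within-subject CV 21%, 90% power, and a lower 95% confidence limit above 1.00 (one-sided 0.025).

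- SD of the log difference = √(2·ln(1 + 0.21²)) = √(2 × 0.04316) = 0.294
- ln(1.28) = 0.247
- Noncentrality at n = 18: 0.247 / (0.294/√18) = 3.56
- Power by the noncentral t: 91.9% with 17 df, 91.7% with the crossover's 16 df
- Smallest n reaching 90% (n − 1 df): 17; with 10% drop-out, 17/0.9 = 18.9, so 19

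The stated 18 is reproduced to within one subject. The sample size is not the problem here.

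**Who can satisfy each rule.** Sequence sizes and products come from SAP Table 1 and the day-by-day table in Protocol 6.2.2. Nicotine profiles are taken only around the single uses on Days 1 and 3 (Protocol 7.5.1.2), so CC smoked freely on Day -1 yields no PK parameter.

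| Sequence | Products on Days 1 and 3 | Planned n | Group (Table 1) |
|---|---|---|---|
| 1 | THS 2.2, CC | 22 | 1 |
| 2 | CC, THS 2.2 | 22 | 1 |
| 3 | THS 2.2, NRT gum | 9 | 2 |
| 4 | NRT gum, THS 2.2 | 9 | 2 |

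With the Table 1 labels:

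- 11.6.1 and 11.6.2.1.1 (Group-1, THS 2.2 and CC): 22 + 22 = 44 of 44
- 11.6.2.1.2 as written (Group-2, THS 2.2 and CC): 0 + 0 = 0 of 18
- 11.6.2.1.2 with gum named in place of CC: 9 + 9 = 18 of 18

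With the labels of SAP 10.1 taken literally:

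- 11.6.2.1.2 as written selects the 44 CC-sequence subjects, none of whom has gum data
- The primary rule in 11.6.1 (Group-1, THS 2.2 and CC) selects 0 of 18

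Under neither labelling can a subject who meets the written rule contribute to a THS 2.2:gum ratio. The two errors also hide each other: read with the 10.1 labels, the product pair in 11.6.2.1.2 looks consistent with its group.

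**Which label is the odd one out.** SAP 10.1 stands alone. Ten other places agree with Table 1: Protocol 6.3, 12.1 and 12.6.3, and SAP 5.1, 5.2, 6.3.1, 11.6.1, 11.6.2.1 (by implication), 11.6.2.1.1 and 11.6.2.1.2.

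**The case against.** The strongest reply is that this is an erratum whose meaning nobody could miss. The heading of 11.6.2.1.2, its opening restriction to Group-2, the ratio, the hypotheses and the t_max difference all name gum. Protocol 12.6.3 states the same tests with no CC condition, and section 5 of the SAP already makes Table 1 the authority on groups. Both documents also say that no claim rests on individual tests (Protocol 12.1.5, SAP 11.1.7). All of this stands. It is why the matter is a drafting error and not a lost analysis.

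A second reply also stands: requiring both products hardly matters in this model. Subject is a fixed effect, so a subject with one product is absorbed by that subject's own parameter. For example, 16 completers give 32 observations less 18 parameters (16 for subjects and sequence, 1 for period, 1 for product), or 14 residual df. Adding two one-product subjects gives 34 − 20 = 14. The ratio, its interval and the test do not change; only the product least-squares means could. Correcting or ignoring the sentence therefore gives the same test. Following it gives none.

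The documents also give no database lock date, so an amendment before lock may no longer be possible.

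None of this removes the contradiction. These sentences select subjects for hypothesis tests, and an analyst should not have to overrule one of them by inference.

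**Conclusion.** The concern holds in both parts. As written, 0 of 18 planned subjects qualify for the five ANOVA parameters of the gum comparison, two of which are formally tested. With gum named, 18 of 18 can. SAP 10.1 reverses labels that Table 1 and ten other places use consistently.

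The counts are planned numbers, before drop-out, and assume that each subject uses the products of the assigned sequence. The SAP does not say whether the inclusion sentence also governs t_max, so that analysis is not counted. The primary comparison with CC is unaffected under the Table 1 labels. The failure would show up as an empty or non-estimable analysis, not as a wrong estimate. It is no flaw of design or power, but it is worth correcting before the analysis is programmed.

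**What to change.** Make two edits in one SAP amendment:

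- In 11.6.2.1.2, require evaluable data for THS 2.2 and NRT gum instead of THS 2.2 and CC.
- In 10.1, define Group-1 PK as the THS 2.2 vs CC comparison (sequences 1 and 2) and Group-2 PK as the THS 2.2 vs NRT gum comparison (sequences 3 and 4).

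SAP section 3 provides for amendments before database lock. Version 2.0 already records the correction of a typing error in the CYP2A6 formula, so there is a precedent. If the database has been locked, state the same two corrections in the clinical study report, where section 3 sends changes to the described analyses.

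The cost is two wording changes. Data, model, sample size and intended populations stay as they are.

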11.6.2.2 Biomarkers

11.6.2.2.1 Exhaled CO and COHb

COHb measured in blood and exhaled CO will be investigated as a measure of exposure to CO.

CO in exhaled breath will be measured using the Smokerlyzer® device, such as the Micro+TM Smokerlyzer® device or similar, once on Day -1 and Day 4. On Days 1 and 3, the first test per day will be performed within 15 minutes prior to T₀ and then between 12:00 PM and 01:30 PM, between 4:00 PM and 05:30 PM, and between 8:00 PM and 09:30 PM. On the wash-out days (Day 0 and Day 2) it will be conducted between 8:00 AM and 09:30 AM, 12:00 PM and 01:30 PM, between 4:00 PM and 05:30 PM, and between 8:00 PM and 09:30 PM.

Analysis of the COHb measurement will be performed at a local laboratory using blood samples taken at specified timepoints. A total of 5 blood samples will be taken per single use day. The first sample will be taken within 15 minutes prior to T_0 . Thereafter the sampling times in relation to T_0 are at 15 minutes, 60 minutes, 4 hours, 12 hours post T_0 .

Statistical Analysis Plan Final v 2.0 / 07 April 2014 Confidential
Page 48 of 73

Descriptive statistics summarized by exposure will be produced separately for all scheduled timepoints for exhaled CO and COHb assessments at single use day. This will be done on the PK populations, overall and by the two stratification factors (sex, CC nicotine level at Admission) as specified in Section 11.1.1 "Stratified Presentation".

Actual values of blood COHb and levels of exhaled CO will be listed and summarized. The number of subjects with COHb levels ≤2% will be summarized for each measurement. The 2% threshold is important because, as reported in (WHO, 2010), COHb elevated above 2% was found to cause ST-segment changes and decreased time to angina.

In addition line graphs will be produced for exposure means (and 95% CI) over all timepoints.

Values of exhaled CO measured during wash-out, Admission, and discharge will not be analyzed because they will be collected only for monitoring purposes, however they will be reported as described in Section 11.4 "Measurements of Product Compliance".

The analysis of the exhaled CO during single use and log transformed blood COHb levels will be performed using a mixed effects ANOVA with a restricted maximum likelihood (REML) method to estimate mean differences and variances separately for THS 2.2 vs CC and THS 2.2 vs NRT gum, using heterogeneous compound symmetry covariance structure in order to allow unequal variances at the different timepoints (**Brown and Prescott, 1999**). Subjects nested within sequence will be used as a random effects and sequence, period, product and product*time point as fixed effect factors. The model will be evaluated including all of the different assessment timepoints, excluding the assessment prior to T₀, In addition, time point will be treated as a repeated measurement.

The SAS code to be used is shown below:

```
Proc mixed data=_data__ method=reml maxiter=200;
Class subject sequence product period;
Model log_COHb (or CO) = sequence period product time_point
product*time_point;
Random subject(sequence);
Repeated time_point / subject=subject*product type=csh;
Lsmean product / pdiff =control('CC/NRT') alpha=0.05 cl;
Lsmean product*time_point / pdiff alpha=0.05 cl;
Run;
```

In case of model convergence issues, this will be reported in the study report and additional covariance structures will be investigated with the following order: heterogeneous autoregressive(type=arh), variance component (type=vc), and unstructured (type=un).

For the analysis of CO breath test, the main comparison will be the difference over all time points. LS means for each product, the overall difference (THS 2.2 - CC or THS 2.2

Statistical Analysis Plan Final v 2.0 / 07 April 2014 Confidential Page 49 of 73

- NRT gum as appropriate) and the differences at each time point will be presented in the tables as a point and interval (95% CI) estimate. Figures of the LS mean difference and 95% CI at each time point will be produced.

For the COHb analysis, the main comparison will be the ratio over all time points. LS means for each product will be back-transformed by exponantiation and presented in tables together with the point and interval (95% CI) estimate of the overall ratio (THS 2.2:CC or THS 2.2: NRT gum as appropriate) and of the ratios at the different time points. Figures of the LS mean ratio and 95% CI at each time point will be produced.

TFL number	Title
TABLES	0.0000
15.2.4.7	Analysis of Blood COHb (%) – PK Population
15.2.4.8.1	Descriptive Statistics of Blood COHb (%) Continuous Measurements – PK Population
15.2.4.8.1.1	Descriptive Statistics of Blood COHb (%) by Sex – PK Population
15.2.4.8.1.2	Descriptive Statistics of Blood COHb (%) by Nicotine Level – PK Population
15.2.4.8.2	Descriptive Statistics of Blood COHb (%) Categorical Measurements – PK Population
15.2.4.9	Analysis of Exhaled CO (ppm) During Single Use – PK Population
15.2.4.10.1	Descriptive Statistics of Exhaled CO (ppm) During Single Use
	Continuous Measurements – PK Population
15.2.4.10.1.1	Descriptive Statistics of Exhaled CO (ppm) During Single Use by Sex – PK Population
15.2.4.10.1.2	Descriptive Statistics of Exhaled CO (ppm) During Single Use by Nicotine Level – PK Population
15.2.4.10.2	Descriptive Statistics of Exhaled CO (ppm) During Single Use Categorical Measurements—PK Population
15.2.4.11.1	Descriptive Statistics of Exhaled CO (ppm) During Days -1, 0, 2 and 4 Continuous Measurements – PK Population
15.2.4.11.1.1	Descriptive Statistics of Exhaled CO (ppm) During Days -1, 0, 2 and 4 by Sex – PK Population
15.2.4.11.1.2	Descriptive Statistics of Exhaled CO (ppm) During Days -1, 0, 2 and 4 by Nicotine Level – PK Population
15.2.4.11.2	Descriptive Statistics of Exhaled CO (ppm) During Days -1, 0, 2 and 4 Categorical Measurements—PK Population
FIGURES	Categorical ineastrements—1 ix 1 optilation
15.1.2.6.1	Blood COHb (%) Profiles Geometric Mean and 95% CI – Group-1 PK Population
15.1.2.6.2	Blood COHb (%) Profiles Geometric Mean and 95% CI – Group-2 PK Population

Statistical Analysis Plan Final v 2.0 / 07 April 2014 Confidential
Page 50 of 73

TFL number	Title
15.1.2.7.1	Blood COHb (%) Profiles Geometric Least Squares Mean Ratio and 95%
	CI – Group-1 PK Population
15.1.2.7.2	Blood COHb (%) Profiles Geometric Least Squares Mean Ratio and 95%
	CI – Group-2 PK Population
15.1.2.8.1	Exhaled CO (ppm) Profiles During Single Use Arithmetic Mean and
	95% CI – Group-1 PK Population
15.1.2.8.2	Exhaled CO (ppm) Profiles During Single Use Arithmetic Mean and
	95% CI – Group-2 PK Population
15.1.2.9.1	Exhaled CO (ppm) Profiles During Single Use Arithmetic Least Squares
	Mean Differences and 95% CI – Group-1 PK Population
15.1.2.9.2	Exhaled CO (ppm) Profiles During Single Use Arithmetic Least Squares
	Mean Differences and 95% CI – Group-2 PK Population
LISTINGS	
15.3.3.4	Listing of Blood COHb Levels (%) and Sampling Times - Safety
	Population
15.3.3.5	Listing of Exhaled Breath CO (ppm) and Measurement Times - Safety
	Population

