For subjects on NRT gum: A total of 16 blood samples will be taken for a 24-hour profile (Day 1 and Day 3). The first blood sample will be taken within 15 min T_0 , Thereafter in relation to T_0 : T_1 ' after 10 min + 1 min, T_2 ' after 20 minutes + 1 min, T_3 ' after 25 minutes + 1 min, T_4 ' after 30 minutes + 1 min, T_5 ' after 35 minutes + 1 min; T_6 ' after 40 minutes + 1 min; T_7 ' after 45 minutes + 1 min, T_8 ' after 60 minutes + 3 min, T_9 ' after 2 hours + 5 min, T_{10} ' after 3 hours + 5 min, T_{11} ' after 4 hours + 5 min, T_{12} ' after 6 hours + 5 min, T_{13} ' after 9 hours + 5 min, T_{14} ' after 12 hours + 5 min, and T_{15} ' after 24 hours + 5 min (this sample will be drawn during the day following product use, i.e., wash-out).

g: COHb blood samples to be taken as follows:

Single use: A total of 5 blood samples will be taken. The first sample within 15 minutes prior to T₀ (start of single product use); thereafter in relation to T₀ at 15 min +2 min, 60 min +3 min, 4 hours +5 min and 12 hours +5 min

- h: A CO breath test will be conducted once on Day -1 and Day 4. On Day 0, Day 1, Day 2, Day 3, four breath tests will be done per day. On Day 1 and Day 3, the first test per day will be performed within 15 minutes prior to T₀ (T₀ = start of first product use) and then around 12:00 pm, 4:00 pm and 8:00 pm. On the wash-out days (Day 0 and Day 2) it will be conducted around 8:00 am, 12:00 pm, 4:00 pm, and 8:00 pm.
- i: QSU-brief will be assessed as follows:

Single use: The QSU-brief will be completed by the subject himself/herself at single use study days.

Philip Morris Products S.A. Statistical Analysis Plan Confidential
Protocol ZRHR-PK-02-JP Final v 2.0 / 07 April 2014 Page 73 of 73

THS 2.2 and CC arms: First sample within 15 min prior to T_0 , 9 assessments thereafter in relation to T_0 : 15 min, 30 min, 45 min, 60 min, 2 hr, 4 hrs, 6 hrs, 9 hrs, and 12 hrs after T_0 with a time window of 10 minutes each.

NRT arm: First sample within 15 min prior to T_0 , 9 assessments thereafter in relation to T_0 : 20 min, 30 min, 45 min, 60 min, 2 hr, 4 hr, 6 hrs, 9 hrs, and 12 hrs after T_0 with a time window of 10 minutes.

- j: Visual analogue scale, three Likert scales and one open question. Cough questionnaire should be asked on Day 0 between 06:30 and '09:00, on Day 2 24 hours after T₀ of Day 1, on Day 4, 24 hours after T₀ of Day 3, and on Day 1 and Day 3, prior product use.

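### The mixed-model code for QSU-brief, COHb and exhaled CO names no denominator-df method, and its variance-component fallback would drop any within-day correlation (minor)

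*SAP*

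**What the plan says.** SAP 11.6.2.2.1 gives REML mixed-model code for exhaled CO and log COHb, fitted separately for THS 2.2 against CC and against NRT gum. The model line is "Model log_COHb (or CO) = sequence period product time_point", followed by the product-by-time interaction. It carries no df option, and neither document names a df method.

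The random-effects line is "Random subject(sequence" in brackets, with nothing at the level of subject by period. Correlation within a single-use day is modelled only in the REPEATED statement, "using heterogeneous compound symmetry covariance structure in order to allow unequal variances at the different timepoints" (CSH).

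For convergence trouble the SAP says "In case of model convergence issues, this will be reported in the study report" and lists the alternatives in order: "heterogeneous autoregressive(type=arh), variance component (type=vc), and unstructured (type=un". The CLASS list is "Class subject sequence product period", without time_point.

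Section 11.6.2.3.1 uses the same model for the QSU-brief total and factor scores. For all three endpoints the main comparison is the product difference or ratio over all time points, with its 95% CI. Section 11.6.3 adds a percentile bootstrap for QSU-brief, but not for COHb or exhaled CO.

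**The concern.** In a two-period crossover, a product contrast averaged over the day rests on one between-period difference per subject. In Group-2 that is 18 differences. A residual df count treats the repeated readings as if they added information on that contrast, so the t multiplier is too small.

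The fallback raises a different question. Under CSH the REPEATED statement carries the within-day correlation. Under VC it does not, and the random subject effect is shared by both periods and cancels from the product contrast. Any positive correlation among readings on the same day then goes unmodelled, and the standard error of the main comparison is understated.

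At stake are the error bars on three secondary endpoints. The point estimates are not in question.

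**Working it through.** The plan gives no figure to reproduce on this point.

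**Inputs.** n = 44 in Group-1 and 18 in Group-2 (SAP 6.1, Table 1). Time points after T0: m = 9 for QSU-brief (SAP 7.3.2), 4 for COHb and 3 for exhaled CO (SAP 11.6.2.2.1). Dropout is assumed to be no larger than 10% (SAP 8), so about 16 completers in Group-2. The calculation takes time_point as a classification factor, which the text intends.

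**Part 1: degrees of freedom.** There are 2nm observations, and the fixed effects plus subjects have rank n + 2m. A residual default therefore gives 2nm - n - 2m.

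- Group-2: QSU-brief 324 - 36 = 288; COHb 144 - 26 = 118; exhaled CO 108 - 24 = 84.
- Group-1: 792 - 62 = 730; 352 - 52 = 300; 264 - 50 = 214.

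With equal variances and constant within-day correlation the contrast has n - 2 df: 16 in Group-2 and 42 in Group-1. The shortfall in CI width is 1 - t(0.975, residual df) / t(0.975, n - 2). Coverage is the probability that |t| on n - 2 df lies below the residual-df quantile.

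| | Residual-df t | t on n - 2 df | CI too narrow by | Coverage |
|---|---|---|---|---|
| Group-2 QSU-brief | 1.9682 | 2.1199 | 7.2% | 93.3% |
| Group-2 COHb | 1.9803 | 2.1199 | 6.6% | 93.5% |
| Group-2 exhaled CO | 1.9886 | 2.1199 | 6.2% | 93.6% |
| Group-1 QSU-brief | 1.9632 | 2.0181 | 2.7% | 94.4% |
| Group-1 COHb | 1.9679 | 2.0181 | 2.5% | 94.4% |
| Group-1 exhaled CO | 1.9711 | 2.0181 | 2.3% | 94.5% |

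With 16 completers the Group-2 shortfall is 7.1-8.2%. With unequal variances, which CSH allows, it is smaller: SDs rising from 0.6 to 1.6 over the day (assumed) give 18.6-22.7 df and a 4.0-6.1% shortfall in Group-2. If the software used 32 df the shortfall would be 3.9%; if it used 16 there would be none.

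**Part 2: the VC fallback.** Let r be the within-day residual correlation, with equal variances scaled to 1. The documents give no value, so r is assumed. The true variance of the contrast is proportional to 1 + (m - 1)r. VC replaces it with a pooled mean square: n - 2 df at 1 + (m - 1)r, and the remaining residual df at 1 - r.

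- QSU-brief, n = 18, r = 0.3: true 1 + 8(0.3) = 3.4; pooled (16 x 3.4 + 272 x 0.7)/288 = 0.85. The model SE is sqrt(0.85/3.4) = 0.50 of the true SE.
- COHb, same setting: true 1.9; pooled (16 x 1.9 + 102 x 0.7)/118 = 0.863; ratio 0.67.
- Exhaled CO, same setting: true 1.6; pooled (16 x 1.6 + 68 x 0.7)/84 = 0.871; ratio 0.74.
- Any endpoint at r = 0: the pooled and true values are both 1, so nothing is lost.

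Simulated coverage of the nominal 95% CI in Group-2 (300,000 draws per setting):

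| Assumed r | QSU-brief | COHb | Exhaled CO |
|---|---|---|---|
| 0 | 95% | 95% | 95% |
| 0.1 | 85% | 91% | 92% |
| 0.3 | 67% | 82% | 85% |
| 0.5 | 55% | 72% | 78% |

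A df correction alone does not repair this. QSU-brief at r = 0.3 judged on 16 df still covers only 71%.

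**Part 3: CLASS.** The code uses time_point in REPEATED and in the product-by-time LS means, both of which need it as a class variable. As printed, the code does not run the analysis that the text describes. This is a slip and does not bear on CI width.

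**The case against.** The case against giving this weight is substantial.

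- **No decision depends on it.** The objectives for these endpoints are descriptive (SAP 5.2), success is defined on nicotine Cmax and AUC(0-last) only (5.4.2), and no claims rest on individual tests (11.1.7). This stands and caps the grade.
- **The df default is software behaviour, and the code is visibly a template.** Silence is not a decision to use residual df. This stands as a limit on certainty. But a SAP that prints its code leaves the choice to the default unless it says otherwise.
- **For QSU-brief the direction under CSH is not fixed.** If correlation decays over the day (assumed 0.8 or 0.6 per hour, with or without a constant 0.3), the CSH standard error is 1.06-1.21 times the true one, and coverage at 0.8 and n=18 is 97.7%. A df correction would then widen an interval that is already too wide. This stands for QSU-brief; for COHb and exhaled CO the same ratio stays at 0.99-1.01.
- **VC is remote.** It needs convergence issues in both CSH and ARH. None of 8,000 simulated CSH fits on complete data failed, and the SAP promises to report such issues. This stands, although reporting an issue does not correct the interval.
- **QSU-brief, where VC does most harm, has a bootstrap.** It keeps the number of subjects per sequence. If subjects are the resampling unit, as that suggests, within-day correlation is preserved and a poor VC interval would show up. COHb and exhaled CO have no such check.

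A reader might infer that ARH is faulty too, because it assumes equal spacing while COHb is sampled at "15 minutes, 60 minutes, 4 hours, 12 hours post" T0 and QSU-brief at "15 min, 30 min, 45 min, 60 min, 2 hr, 4 hrs, 6 hrs, 9 hrs, and 12 hrs". The documents do not support that: the sign and size of any ARH error depend on a correlation they do not give.

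**Conclusion.** Minor. The planned CSH model does account for correlation within a day, so the missing df method causes only a small shortfall: 6.2-7.2% of CI width in Group-2 and 2.3-2.7% in Group-1. That assumes residual df, equal variances and constant correlation. It is smaller with unequal variances, and for QSU-brief decaying correlation may offset it.

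The VC fallback is the larger error, but a conditional one. It arises only if CSH and ARH both have convergence issues, and only if within-day correlation is positive, which is plausible but not stated. A reader might infer that a VC interval is always too narrow, or that the reported intervals will have coverage near 55%. Neither follows: there is no loss at zero correlation, and nothing indicates that VC will be reached. The study's success criterion and its nicotine conclusions are untouched.

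**What to change.** In the code of SAP 11.6.2.2.1, which 11.6.2.3.1 also uses:

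1. Add ddfm=kr (Kenward-Roger) to the MODEL statement.
2. Add time_point to CLASS.
3. Replace the bare VC fallback with compound symmetry (type=cs), or keep VC and add a subject-by-period random effect. With complete balanced data and a positive subject variance, compound symmetry gives the overall contrast the same SE as an analysis of each subject's day means, whatever the within-day correlation.

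The cost is a few lines of code. With equal variances, Group-2 CIs widen by 6.6-7.7% at n=18 (7.6-8.9% with 16 completers) and Group-1 CIs by 2.4-2.8%; with unequal variances they widen by less. The type=cs fallback gives up unequal variances over time, which affects the per-time-point estimates, but the VC structure it replaces gives them up as well.
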